## 4 OVERALL DESIGN AND PLAN OF THE STUDY

### 4.1 Overall Design

This is an open label study in approximately 6 subjects in 2 centers to assess the safety, PK, and efficacy of the maximum tolerable dose (MTD) of oral miglustat (100 mg once daily [QD] to 200 mg 3 times daily [TID]) in subjects  $\geq$  17 years of age with CLN3 disease..

The study sites are Texas Children's Hospital (TCH) and National Institutes of Health Clinical Center (NIH CC):

- Screening, enrollment, and end-of-treatment visits for follow-up safety assessments will be conducted by TCH. Eligibility will be confirmed by TCH after all inclusion/exclusion criteria are assessed; enrollment decision will be communicated to subject via telephone call by TCH. If the subject is eligible, the study staff will schedule NIH CC baseline visit. TCH will also review all subject safety data throughout the duration of the study.
- Baseline, every 6 months visit for efficacy assessments will be conducted at NIH CC.
- Additional safety assessments will be performed at the Local Health Center / Subject's Home and at the NIH CC as per protocol.

This study includes a dose-titration period of 9 weeks.

Once the dose titration and PK sampling period is completed, subjects will continue their MTDs during the maintenance period. Temporary or permanent dose reductions for tolerability are permitted at any time during the remainder of the study in the dose increments shown in [Section 6.2](#). As not all subjects will have the same duration of treatment, additional safety phone calls and visits will be organized as need at regular timepoints for patients with longer duration of treatment.

Safety will be assessed at all study visits, and safety labs will be collected at baseline, during titration at Week 6 and every 6 months during maintenance phase. The TCH Principal Investigator (PI) will also conduct monthly telephone safety checks during the dose-titration period and every 2 to 4.5 months calls thereafter to discuss adverse events (AEs).

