#### **5.4.2 Participant Discontinuation**

The participation of an individual subject may be discontinued prematurely for reasons such as:

- Any condition which in the opinion of the investigator no longer permits safe participation in the study, in particular, if a participant develops a CTCAE Grade 3 or higher (See section 7.1.1.1). Participants who develop symptoms such as numbness and tingling should have a careful re-assessment of the risk/benefit of therapy and cessation of treatment may be considered.
- Subject becomes pregnant
- Lack of study compliance

A subject may discontinue participation in the clinical study at his/her own request at any time without stating a reason.

At the time of discontinuing from the study, if possible, an early termination visit and a 30-day end of study visit should be conducted, as shown in the schedule of activities. If not possible, a remote visit could be organized via telemedicine for applicable evaluations or at least a phone contact will be established with the participant or the caregiver to collect safety information (AEs). See schedule of activities for data to be collected at the time of study discontinuation and follow-up and for any further evaluations that need to be completed.

The reason for withdrawal of the subject must be documented by the investigator together with all data collected until the day of premature study discontinuation including laboratory results and assessment of AEs.

Subjects who withdraw or are withdrawn from the study before exposure to the study drugs or during the titration period may be replaced.

If a participant withdraws from the study, he/she may request destruction of any remaining samples taken and not tested, and the investigator must document any such requests in the site study records and notify the sponsor accordingly. If the participant withdraws from the study and also withdraws consent for disclosure of future information, no further evaluations should be performed and no additional data should be collected. The sponsor may retain and continue to use any data collected before such withdrawal of consent. Lack of completion of all or any of the withdrawal/early termination procedures will not be viewed as protocol deviations so long as the participant's safety was preserved.

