#### 4 ANALYSIS POPULATIONS

The **Safety Population** will consist of all subjects who enroll in the study and receive at least 1 dose of study medication.

The **PK Population** will consist of subjects who received at least 1 dose of study drug and had a full PK sample set drawn per protocol for that day.

PK Population is used for all PK analyses. PK analyses are performed by [REDACTED] PK group, described in PK Analysis Plan, and reported in PK Analysis Report. PK analyses are not in scope of this SAP.

The **Efficacy Population** will consist of the subjects who received at least 1 dose of study medication and had at least 1 follow-up efficacy assessment, defined as at least one post-baseline Unified Batten Disease Rating Scale assessment.

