### **5.2.2 Seizure Frequency**

Seizure frequency will be collected in subject diaries and all seizures reported in the diaries will also be reported as AEs on the adverse events eCRF page.

For the purpose of summarizing seizures, the more granulated information from AE pages will be used. Each AE with preferred term including the word "seizure" will be considered a seizure for the purpose of this analysis.

For each subject the number of seizures per the following 3-month intervals will be calculated:

1. Pre-treatment,
2. Baseline to month 3 (study days 1 to 90; both inclusive),
3. 4 to 6 months (study days 91 to 180; both inclusive),
4. 7 to 9 months (study days 181 to 270; both inclusive),
5. 10 to 12 months (study days 271 to 360; both inclusive),
6. 13 to 15 months (study days 361 to 450; both inclusive),
7. 16 to 18 months (study days 451 to 540; both inclusive),
8. After 18 months (study day 541 and onwards),
9. Entire study duration (all previous combined).

Qualifying AE start days will be compared with the study days above to determine in which time interval the seizure occurred. For study day 1, treatment start time and AE start time will additionally be compared. In case of missing or partial AE start dates, imputation rules provided in section [8.1](#) will be used for determining the interval in which the seizure occurred.

Summary statistics of seizure counts for all subjects in the Efficacy Population will be provided by time interval. Individual seizure counts by time interval will be provided in a listing.

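### SAP 5.2.2 summarises raw seizure counts per interval without regard to days observed, so unequal or ended follow-up is read as fewer or more seizures, most clearly after day 540

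*SAP*

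**What the plan says.** Seizure frequency is a secondary efficacy endpoint. SAP 5.2.2 defines it in four steps:

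- **Quantity.** "For each subject the number of seizures per the following 3-month intervals will be calculated". The list has a pre-treatment interval, six 90-day intervals covering study days 1 to 540, an open-ended last one given as "After 18 months (study day 541 and onwards" in the SAP, and a total over the whole study.
- **Source.** The count comes from the adverse event pages, not directly from the diary: "Each AE with preferred term including the word 'seizure' will be considered a seizure for the purpose of this analysis".
- **Allocation.** "Qualifying AE start days will be compared with the study days above to determine in which time interval the seizure occurred". The date on which observation ended is not an input.
- **Summary.** "Summary statistics of seizure counts for all subjects in the Efficacy Population will be provided by time interval". Individual counts by interval are also listed.

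Three other provisions matter. SAP 4 admits a treated subject to the Efficacy Population on one follow-up efficacy assessment, "defined as at least one post-baseline Unified Batten Disease Rating Scale assessment", and nothing removes that subject later. SAP 5.1.1 has adverse events recorded only until the end of study visit. Protocol 4.1 expects unequal follow-up ("As not all subjects will have the same duration of treatment"), and the synopsis allows treatment for up to 116 weeks, ending when the early access program starts.

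**The concern.** A count of adverse event records cannot separate a subject who had no seizures from one whom nobody was observing: both produce no records. A visit-based measure leaves a visible gap when a visit is missed, but this derivation returns a valid-looking 0. A short interval likewise returns a small number and a long one a large number at the same underlying rate.

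The endpoint is read as a time course in a single arm of six, with no control group to expose an artefact of follow-up. A falling mean could reflect people leaving. The last interval could rise or fall according to when each subject moved to early access. Elsewhere the SAP treats absent information conservatively: missing UBDRS items take the worst score, and adverse events with missing severity are set to Grade 3. Here, absence would take the best possible value.

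**Working it through.** The documents give no seizure rate, dropout rate or target figure, so there is no stated result to reproduce. The rates and departures below are assumptions. Each subject's rate is held constant, so any movement is an artefact.

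**Inputs from the documents**
- Six subjects (SAP 2.2).
- Day 57 is Week 9 (Protocol Table 1-3), so Week w starts on day 7(w − 1) + 1. Week 26, when the first post-baseline UBDRS is due, is day 176. Week 78 is day 540. Both visits have a window of ± 1 month.
- Maximum treatment is 116 × 7 = 812 days.

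**1. The interval after 18 months (no dropout needed)**

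The longest on-treatment time in this interval is 812 − 540 = 272 days. The shortest is 0, for a subject who moves to early access at about Week 78. Expected count = 3 × days / 90:

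| Days observed after day 540 | Count at 3 per 90 days |
|---|---|
| 0 | 0 |
| 7 | 0.23 |
| 90 | 3.00 |
| 182 | 6.07 |
| 272 | 9.07 |

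The rate is 3 per 90 days in every row with any observation. In the first row it is unknown.

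**2. The pre-treatment interval**

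Screening to first dose is nominally up to 42 days, or about 4 weeks in the synopsis. At the same rate the count is 3 × 42/90 = 1.4, or 3 × 28/90 = 0.93, against 3.0 in a 90-day treated interval. Raw counts would therefore suggest a rise after treatment starts where there is none.

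**3. Days 181 to 540, if someone leaves after day 180 (assumed)**

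Equal rates of 3 per 90 days:
- One leaver: 5 × 3/6 = 2.5, and 2.5/3 − 1 = −16.7%.
- Two leavers: 4 × 3/6 = 2.0, and 2.0/3 − 1 = −33.3%.
- The median stays at 3.0 in both cases. The percentages are the same for any equal non-zero rate (1 and 10 were also checked).

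Unequal rates of 0, 1, 2, 3, 6 and 12 per 90 days (mean 24/6 = 4.0, median 2.5), one leaver:

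| Leaver's rate | Mean with leaver as 0 | Change | Mean of the five remaining |
|---|---|---|---|
| 0 | 4.00 | 0% | 4.8 |
| 1 | 3.83 | −4.2% | 4.6 |
| 2 | 3.67 | −8.3% | 4.4 |
| 3 | 3.50 | −12.5% | 4.2 |
| 6 | 3.00 | −25.0% | 3.6 |
| 12 | 2.00 | −50.0% | 2.4 |

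If the subject with rate 12 leaves, the values become 0, 0, 1, 2, 3, 6 and the median falls from 2.5 to 1.5. If the subject with rate 1 leaves, they become 0, 0, 2, 3, 6, 12 and it stays at 2.5. The last column shows that omitting leavers also moves the mean when rates differ. Within-subject change is 0 for all five who remain, in every row.

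**4. A partly observed interval**

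At 3 per 90 days, a subject leaving at day 225 is seen for 45 of the 90 days in the 181–270 interval and contributes 1.5. Mean count: (5 × 3 + 1.5)/6 = 2.75. Seizures per 90 observed days: 16.5/(5 × 90 + 45) × 90 = 3.0.

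**The case against.** The strongest reply is that no passage says a departed subject is scored 0. SAP 5.12 summarises continuous variables over subjects with evaluable data, and SAP 7.2.4 separates the population N from the n with data available. On that view, the reference to all Efficacy Population subjects only names the analysis set, and a careful programmer would leave departed subjects out. This stands to the extent that zero-scoring is a consequence of the literal derivation and not a stated rule. It does not close the gap. The SAP never says when a seizure interval is evaluable, a record count is never missing, and nothing in either section deals with partly observed or unequal intervals.

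Second, attrition is hypothetical. The documents report no death or withdrawal. SAP 6 says all six subjects completed titration, and Protocol 5.4.1 describes permanent discontinuation as rare and distinguishes stopping drug from leaving study procedures. This stands. Exits are allowed ("A subject may discontinue participation in the clinical study at his/her own request at any time without stating a reason"), but their number is unknown. The differing durations in Protocol 4.1 arise mainly after Week 78, so they support unequal follow-up in the last interval and not in days 181 to 540.

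Third, the analysis is descriptive, SAP 5.12 also reports median, minimum and maximum, and individual counts and disposition are listed. With six subjects a reader could often spot a false zero. This limits the harm, but the seizure listing is not required to show observed days, so a zero there is ambiguous too.

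**Conclusion.** The concern holds in a limited form. SAP 5.2.2 takes no account of time observed. For the interval after 18 months this matters by design: follow-up there can run from about 0 to 272 days, so raw counts are not comparable between subjects or with the 90-day intervals. The pre-treatment interval has the same problem because it is shorter. For days 181 to 540 the effect is conditional: −16.7% in later means for one leaver of six and −33.3% for two, if rates are equal and non-zero; 0% to −50% for one leaver in the unequal example. It rests on assumed rates and departures.

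A reader might go further and infer that the plan deliberately scores leavers as seizure-free, that the most affected subjects will be the ones to leave, or that a declining mean must be attrition. The documents do not support these readings. They state no zero rule, report no departures and say nothing about who leaves. Larger falls can be produced by assuming one leaver with very frequent seizures, but that would be a property of the invented example.

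**What to change.** In SAP 5.2.2, before database lock:

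1. For each subject and interval, derive days under adverse event and diary observation. Start from screening for the pre-treatment interval and from first dose for treated intervals. End at the earliest of last study visit, withdrawal, loss to follow-up or death. Stopping drug alone does not end observation.
2. Set the count to missing, not 0, when observed days are zero.
3. Summarise seizures per 90 (or 28) observed days. This puts pre-treatment, partly observed and post-day-540 intervals on one scale and keeps seizures recorded in incomplete intervals.
4. Show n and total observed days per interval, and add observed days to the individual listing.
5. Add within-subject change from the pre-treatment rate, matching the baseline in Protocol 7.3.2 (screening to first dose), because omitting leavers can itself shift the mean.

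The cost is a few sentences of SAP text and modest programming on dates already collected. No protocol change is needed. The price is a smaller n in later intervals and unstable rates where few days are observed, which showing the observed days makes visible.

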### **5.2.3 Vineland Adaptive Behavior Scales, Version 3**

Vineland Adaptive Behavior Scales data will be collected and analyzed by NIH.

For the purpose of this SAP, Vineland Adaptive Behavior Scales data will only be listed.

#### **5.2.4 Ophthalmic Evaluation**

The following ophthalmic evaluation data is collected in the eCRF throughout the study:

1. Visual acuity evaluation performed and result (Normal / Abnormal), if performed,
2. Visual fields evaluation performed and result (Normal / Abnormal), if performed,
3. Optical Coherence Tomography (OCT) evaluation performed and result (Normal / Abnormal), if performed,
4. Intraocular pressure in the left eye (OS) (mm Hg),
5. Intraocular pressure in the right eye (OD) (mm Hg).

Categorical ophthalmic evaluation results will be presented by visit in a frequency table.

Observed values and changes from baseline for intraocular pressure variables will be summarized at each scheduled post-baseline visit. Baseline will be defined as last value collected before first study drug administration; both data collected at scheduled and unscheduled visits will be included in baseline derivation.

Ophthalmic evaluation data collected in the eCRF will be listed.

NIH is collecting and analyzing additional ophthalmic data. That data is only listed for the purpose of this SAP.

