## 2.2 Background

First described in 1826, juvenile Batten (CLN3) disease is an ultra-rare, genetic, lysosomal storage disease that primarily affects the nervous system and, is fatal. Children with CLN3 disease develop normally, even excelling in school until ages 4-7 years, when progressive vision loss becomes noticeable (Bozorg et al., 2009 and Aberg et al., 2011). Concomitantly, or shortly thereafter, parents report personality changes and behavioral issues. Typically, within 2–3 years after symptom onset, total vision loss occurs, and seizures begin. This is followed by declining speech, progressive loss of motor coordination, and cardiac involvement. Psychosis, hallucinations or dementia can appear anytime during the disease. Eventually, children become wheelchair-bound, then bed-ridden, and die in their late teens or early twenties (Bozorg et al., 2009, Aberg 2001, and Ostergaard 2016).

CLN3 disease is not preventable, and although a cure is desperately needed for these patients, no treatment that can slow, halt or reverse the symptoms of CLN3 disease has been identified to date. Therefore, there is a significant unmet medical need for meaningful treatment options for these patients.

On a molecular level, CLN3 disease is the result of loss-of-function mutations in the *CLN3* gene and the absence or dysfunction of its gene product, CLN3 protein. This disease is characterized by lysosomal accumulation of fatty, granular autofluorescent material (ceroid, lipofuscin) within cells of the brain and all other tissues of the body. The normal function of CLN3 protein is unknown;

however, CLN3 deficiency has been linked to defects in microtubule-dependent antero- and retrograde trafficking, autophagy, and endocytosis (Cotman & Staropoli, 2012 and Tecedor et al., 2013).

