Efficacy assessments include UBDRS; seizure frequency (diary); Vineland-3; ophthalmic assessments including visual acuity, visual field (if feasible), and retinal thickness using OCT; and volumetric assessments using MRI. They will be assessed at baseline and during the maintenance period. Baseline OCT will be obtained in all study participants. In those participants with no light perception vision, dense cataracts, or other ophthalmologic findings that produce significant artifacts in the OCT images, OCT imaging will not be repeated.

Blood, urine and cerebrospinal fluid biomarkers of neurodegeneration will also be assessed as exploratory endpoints of treatment activity.

In case of any event precluding safe travel by participants to NIH after the baseline visit, evaluations could be done at the Local Health Center/ Patient's Home (labs, ECG (if feasible), physical exam, vital signs, weight) or via remote methods (history, UBDRS, Vineland-3, adverse events, concomitant meds, seizure diary) or be deferred (+/- 1 month: neurological exam, ophthalmology exam, MRI, lumbar puncture).

After the Week 78 efficacy assessment, patients will continue to be treated with miglustat until they can be included, if they wish to continue to receive the treatment, in the early access program.

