##### 3. VISUAL ACUITY

3.

0 = normal  
1 = mildly impaired  
2 = finger counting only  
3 = light/dark perception  
4 = blind

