### **5.12 General Aspects for Statistical Analyses**

- Categorical variables will be summarized using the number of observations (n), frequency and percentage of subjects. All percentages will be presented as one-decimal point, unless otherwise specified. Percentages equal to 100 will be presented as 100% and percentages will not be presented for zero frequencies.
- Continuous variables will be summarized using the number of subjects with evaluable data (n), mean, standard deviation (SD), geometric mean (where appropriate), median, minimum and maximum. In general, the same number of decimal places as in the raw data will be presented when reporting minimum and maximum, 1 more decimal place than in the raw data will be presented when reporting the mean and median, and 2 more decimal places than in the raw data will be presented when reporting the SD.
- Unless stated otherwise, the percentages will be based on the number of non-missing observations. The column header will still contain the number of subjects in the treatment group. Where appropriate, there will be a row for the number of non-missing observations in the table (at each time point, if required) for each variable being summarized.
- All relevant subject data will be included in listings and sorted by treatment group (treated subjects first, followed by screen failures), subject ID, visit/timepoint, and assessment type, as applicable. All listings (except for study drug exposure) will be based on All Screened Subjects.
- Unscheduled or repeat assessments will not be included in summary tables unless specified. All assessments will be included in the subject listings.
- All tables, listings and figures will include footers that identify the name of the program that created the output, together with the date and time on which it was created. Headers will include the total number of pages that the presentation contains and, for each page, the number of the page within the presentation.

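### The Normal/Abnormal eye tables in SAP 5.2.4 cannot show worsening in subjects who start Abnormal, and the OCT percentages can move because some participants are not re-imaged

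*SAP*

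**What the plan says.** The secondary efficacy objective (protocol section 3; SAP section 3, Table 1) is the effect of treatment on how the disease progresses over time. The eye measures named for it are visual acuity, visual fields and OCT. Protocol 4.1, 7.3 and 7.3.4 identify the OCT quantity as retinal thickness.

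SAP 5.2.4 takes three categorical items from the eCRF:

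- acuity: "Visual acuity evaluation performed and result (Normal / Abnormal), if performed"
- fields: "Visual fields evaluation performed and result (Normal / Abnormal), if performed"
- OCT: "Optical Coherence Tomography (OCT) evaluation performed and result (Normal / Abnormal), if performed"

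The planned display is one line: "Categorical ophthalmic evaluation results will be presented by visit in a frequency table". No shift from baseline and no pairing of subjects is described. Change from baseline is planned for intraocular pressure only. The section ends by saying that NIH collects and analyses further eye data, which this SAP only lists.

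Four other places bear on these tables:

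- **Disease course.** Protocol 2.2 says vision loss is noticed at 4 to 7 years, and adds: "Typically, within 2–3 years after symptom onset, total vision loss occurs, and seizures begin". Inclusion criterion 2 sets entry at 17 years or older.
- **Repeat OCT.** Protocol 4.1 and 7.3.4 require a baseline scan in everyone. They then exempt participants with no light perception, dense cataracts or other "ophthalmologic findings that produce significant artifacts in the OCT images, OCT imaging will not be repeated".
- **Denominator.** SAP 5.12: "Unless stated otherwise, the percentages will be based on the number of non-missing observations".
- **Graded acuity.** UBDRS item 3 (protocol Appendix 2) runs from 0 (normal) to 4 (blind), with intermediate grades such as "3 = light/dark perception". SAP Table 2 uses it inside two physical scores and imputes missing items as 4. SAP 5.2.1 tabulates single items only for the Clinical Summary domain.

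**The concern.** Progression is change within a person. A two-level code registers it only when someone crosses from Normal to Abnormal. A subject who is Abnormal at baseline can lose all remaining function and stay in the same cell. If most subjects start there, a flat row carries almost no information, yet it is easily described in a report as stable.

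The OCT table has a second problem. Who is scanned after baseline depends on the state of the eye, and those not scanned drop out of the percentage. The baseline column describes all participants, while later columns may describe a selected part of them. A by-visit percentage can then move for reasons unrelated to change in any retina. In an open-label, single-arm study of about six subjects, one or two people leaving the denominator is enough to alter the impression given by a named secondary endpoint.

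**Working it through.** **No plan figure to reproduce.** Sample size (six) rests on availability, and neither document gives an expected share Abnormal at baseline. The checks below use the disease course and stated assumptions.

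**1. Age at total vision loss.** Take symptom onset as the age at which vision loss is noticed, 4 to 7 years, and add 2 to 3 years. The earliest is 4 + 2 = 6 and the latest is 7 + 3 = 10. Against the minimum entry age, 17 − 10 = 7 and 17 − 6 = 11. The typical patient would have lost vision at least 7 to 11 years before entry.

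**2. Room to move in a two-level code.** Let p be the assumed chance that a subject is Abnormal at baseline, independent between subjects. The chance that all six start Abnormal is p^6. The expected number who could still cross to Abnormal is 6(1 − p).

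| Assumed p | All six Abnormal | Expected able to cross |
|---|---|---|
| 0.80 | 0.26 | 1.2 |
| 0.90 | 0.53 | 0.6 |
| 0.95 | 0.74 | 0.3 |
| 1.00 | 1.00 | 0 |

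Over this range, about one subject at most is expected to be able to show worsening in a given table.

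**3. OCT denominator.** Suppose a of 6 are Abnormal at baseline, nobody changes, and k Abnormal participants are not re-imaged. The table shows a/6 at baseline and (a − k)/(6 − k) later.

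| Baseline | k = 1 | k = 2 | k = 3 |
|---|---|---|---|
| 6/6 = 100% | 5/5 = 100% | 4/4 = 100% | 3/3 = 100% |
| 5/6 = 83% | 4/5 = 80% | 3/4 = 75% | 2/3 = 67% |
| 4/6 = 67% | 3/5 = 60% | 2/4 = 50% | 1/3 = 33% |

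With mixed baseline results the percentage falls although no one has changed. With all six Abnormal it does not move, and the limit in step 2 is then complete. The direction depends on who leaves: if one Normal participant were not re-imaged, 4/6 (67%) would become 4/5 (80%).

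**4. Does another planned table fill the gap?** Item 3 is one of 28 items in the Physical Assessment score and one of 16 in the modified subscale, each an average over items. A one-grade loss of acuity moves these scores by 1/28 = 0.036 and 1/16 = 0.063, and cannot be told apart from a change in any other item. Retinal thickness has no table in this SAP.

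**The case against.** The strongest reply is that SAP 5.2.4 covers only the eCRF summary. NIH analyses further eye data, and the SAP makes the same division of work for Vineland, MRI and biomarkers. This stands as a limit on scope. A reader might infer that the trial as a whole cannot show eye progression. The documents do not support that, because the NIH analysis is not described and cannot be judged. Nor do they supply the missing assurance: SAP 5.2.4 cites no NIH analysis plan, whereas SAP 5.4 refers to a separate plan for PK.

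Second, the drop in numbers may be visible. SAP 5.12 keeps N in the column header and adds a row of non-missing counts where appropriate, SAP 7.2.5.1 allows a Missing category, and the data are listed. With six subjects a careful reader would notice. That reduces the harm, but it neither pairs the subjects nor gives the reason a scan is absent.

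Third, the two parts of the point partly exclude each other. A false fall in the OCT percentage needs some Normal scans at baseline, and the same disease course makes those less likely. One could push the arithmetic to 4/6 (67%) falling to 0/2 (0%), but that requires two Normal subjects and the loss of every Abnormal one. It is an extreme, not an expectation.

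Fourth, the disease course is described as typical, there is no vision criterion for entry, and the protocol itself allows for residual vision. Six out of six Abnormal is therefore an inference, and a Normal-to-Abnormal change would show.

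Fifth, item 3 may share the ceiling: a subject already at 4 cannot worsen on it either. This also stands, and is why the number at 4 should be reported.

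**Conclusion.** The point holds for the tables planned under SAP 5.2.4. The two-level code cannot show worsening in anyone Abnormal at baseline, which on the protocol's typical course is likely to be most subjects. An unchanged acuity, field or OCT table is not evidence of stability.

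The OCT percentage can also shift through the non-repeat rule and the non-missing denominator. In the assumed examples the fall with nobody changing runs from 3 percentage points (5/6 to 4/5) to 33 (4/6 to 1/3). It is zero if all six are Abnormal. The sizes assume mixed baseline results and that only Abnormal participants are not re-imaged; the documents give neither.

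Three stronger readings should be avoided:

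- **All three tables compare different patients across visits.** The documents state a rule for OCT only. Fields are done if feasible, and acuity has no stopping rule.
- **The worst eyes leave the table.** The rule applies to participants rather than eyes. It also covers cataract and image artifact, which need not mean the worst retina.
- **Intraocular pressure is misplaced among the efficacy measures.** The protocol's eye endpoint is worded as an open list, so no change is asked for there.

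Efficacy is secondary and purely descriptive here, so the consequence is a misleading summary, not a wrong test result. The correction is still worth making before database lock.

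**What to change.** In SAP 5.2.4:

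(a) Restrict the OCT comparison to participants with both a baseline and a post-baseline scan, and present it as a shift from baseline. Add a row at each visit for scans not repeated per protocol, counted out of N. The imaging rule itself need not change.

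(b) Tabulate UBDRS item 3 (0 to 4) as observed value and shift from baseline at each UBDRS visit. Use observed data only: the worst-value imputation in SAP Table 2 would record a missing answer as blindness. State how many subjects are already at 4 at baseline and so cannot worsen.

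(c) If the NIH data transferred for listing include retinal thickness, summarise its within-subject change for the paired participants. The documents do not say what that transfer contains, so this needs confirming first.

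Items (a) and (b) need SAP wording and two small tables from assessments already scheduled. SAP 5.1.2 already uses shift tables for selected laboratory parameters, so the format is not new. The downside is that the evaluable numbers will be openly small and item 3 may be at its ceiling for some subjects. Both are better shown than left inside a percentage.
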